3.1. General Overview

The GAME PAD study is a two-arm randomized controlled trial aimed at evaluating whether a home-based walking program with automated coaching augmented with gamification and behavioral economic principles improves functional capacity in patients with PAD. The study will randomize 100 patients with PAD to a 16-week home-based walking program using goal-setting alone (attention control) or to the same home-based walking program with automated coaching augmented with gamification and behavioral economic principles. There will be a 2-week run-in period to obtain baseline measures of physical activity, followed by a 16-week intervention period, and an 8-week follow-up period (see study protocol figure below).

The study will be conducted using Way to Health, a research information technology platform at the University of Pennsylvania used previously for physical activity behavioral interventions.

After institutional review board (IRB) approval of the study, patients who meet the eligibility criteria will be contacted by email, phone call or letter to invite them to participate. Those who

qualify and express interest will provide online informed consent to the study procedures. All patients will receive a wearable activity tracker (Fitbit Inspire) that will be enrolled in the Way to Health platform. The Fitbit and Way to Health platform will continuously track patients' steps and survey patients regarding pain with walking monthly. Within the Way to Health platform, patients will be randomized to one home-based exercise program or the other. All other management decisions are completely at the discretion of the care providers. Data capture will include:

- **Baseline case report form** (for each patient) collecting clinical information abstracted from the medical record
- **Patient-reported quality of life and functional limitation related to PAD** collected via telephone survey and/or the Way to Health platform at the time of enrollment and at 16- and 24-week follow-up
- **Psychometric features** collected via in-person survey at the time of enrollment
- **Daily step count** and calculated **exercise minutes** collected via FitBit charge
- **Patient-reported pain with ambulation** collected via the Way to Health platform at monthly intervals

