4.4. Randomization

Participants that have established baseline measures and finished goal selection will be randomly assigned to attention control or the automated coaching + gamification intervention using a 1:1 allocation and stratifying on baseline step count (< 2500 steps, 2500 – 5000 steps, > 5000 steps)

with block randomization and block sizes of 2 using an electronic number generator through the Way to Health research technology platform.

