4.6. End-of-Study Questionnaire Completion

At the end of the 16-week intervention, patients will be alerted by the Way to Health platform to return to the website to complete an end-of-study questionnaire consisting of the San Diego Claudication Questionnaire, the Walking Impairment Questionnaire, the Patient-Reported Outcomes Measurement Information System (PROMIS) measures of mobility, pain interference, and satisfaction with social roles and activities, and the SF-36 physical functioning scale. Patients will complete the same questionnaire again 8 weeks later.

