5.3. Data Analyses

Data for all consented patients, whether or not they completed all protocol requirements, will be included for analysis. Patient demographics, risk profiles, clinical characteristics, and baseline questionnaire results will be reported. In addition to change in number of steps from baseline, secondary outcomes will include change in daily exercise minutes, and change the Walking Impairment Questionnaire, the Patient-Reported Outcomes Measurement Information System (PROMIS) measures of mobility, pain interference, and satisfaction with social roles and activities, and the SF-36 physical functioning scale. In exploratory analyses, we will identify baseline psychometric properties associated with greater change from baseline in daily steps, and greater response to the gamification intervention.

All analyses will be performed using intention-to-treat. Data can be missing for any day if the participant did not use the activity tracking device or did not upload data. For the main analysis, we will use multiple imputation for step values that are either missing or for values less than 1000 steps because evidence suggests these are not accurate measures of actual activity. We will perform five sets of imputations and results will be combined using Rubin's standard rules. We will perform sensitivity analyses to assess the robustness of the findings using only collected data with and without step values less than 1000 steps. The primary analysis will fit mixed effects

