regression models to evaluate changes in physical activity outcomes measures adjusting for each participant's baseline step, time at the observation level using calendar month fixed effects, participant random effects, and adjusting for repeated observations of participant step counts. We will compare changes in daily step count and physical activity from baseline to the intervention period, excluding weeks 1-4 (the ramp-up period). We will repeat these analyses, comparing changes in daily step count and physical activity from baseline to the follow-up period. Secondary analyses will fit mixed effects regression models adjusted for other variables of interest such as participant characteristics. Exploratory analyses will fit mixed effects regression models to evaluate associations of participant characteristics or behaviors with strong or poor performance in the outcome measures. In a subgroup analysis, we will separately analyze subgroups reporting and not reporting exertional lower extremity symptoms.

For changes in survey measure scores from baseline to the end of the intervention, and from baseline to the end of follow-up, we will compare the intervention and control arms using paired t-tests, without adjustment for baseline characteristics.

6. Human Research Protection

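### The survey outcomes are to be compared between two independent arms with a paired t-test, but the plan defines no pairs

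*Combined protocol and SAP*

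**What the plan says.** Section 3.1 describes the design: "The GAME PAD study is a two-arm randomized controlled trial". Section 4.4 allocates individual patients "using a 1:1 allocation and stratifying on baseline step count" in three strata, "with block randomization and block sizes of 2 using an electronic number generator".

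Section 5.1 lists the survey measures as secondary outcomes 4 to 6: the Walking Impairment Questionnaire, three PROMIS scales (mobility, pain interference, social roles) and SF-36 physical functioning. Each is a change from baseline to the end of the intervention and to the end of follow-up.

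The only test given for these change scores, at both time points, is in section 5.3: "we will compare the intervention and control arms using paired t-tests, without adjustment for baseline characteristics".

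Three other statements bear on how that sentence could be carried out:

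- On survey collection, section 4.6 says "patients will be alerted by the Way to Health platform to return to the website to complete an end-of-study questionnaire". Section 3.1 also allows collection by telephone.
- On missing data, section 5.3 says "we will use multiple imputation for step values that are either missing or for values less than 1000 steps". It gives no rule for missing surveys.
- On who is analysed, section 5.3 says "Data for all consented patients, whether or not they completed all protocol requirements, will be included for analysis".

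**The concern.** A paired t-test needs each observation in one group to have a defined partner in the other. The natural pair here is a patient's baseline and follow-up score, and subtracting one from the other to get the change already uses it. A second pairing, of an intervention patient with a control patient, would have to be defined, and section 5.3 defines none.

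The sentence can be read in three ways:

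1. A slip for a two-sample t-test on change scores. This is the likeliest.
2. Pairing by the randomisation blocks of 2. A complete block holds one patient from each arm, so this is conceivable, but the analysis section never mentions blocks.
3. A paired test of baseline against follow-up within each arm, with the two results set side by side. This does not test the difference between arms.

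The readings use different data and can give different conclusions. The sentence governs five scores at two time points, ten comparisons in all, which are the trial's only patient-reported efficacy outcomes. A plan fixed in advance should not leave the test to be chosen once the data are in hand.

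**Working it through.** The plan states no power, SD or expected missing rate for any survey score, so there is no figure of its own to reproduce. Its 80% power statement in section 5.2 concerns steps only and does not bear on this point. From the documents I take 50 patients per arm and alpha 0.05 (section 5.2; two-sided assumed) and blocks of 2 (section 4.4). Missing rates, effect sizes and correlations below are assumptions. Effects are in SDs of the change score.

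**Reading 1, two-sample test on change.** With 50 against 50 there are 98 degrees of freedom and a critical t of 1.984. A difference of about 0.57 SD has 80% power. This is the reference case.

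**Reading 2, pairing by block.** With 50 blocks and a proportion m of surveys missing independently:

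- complete pairs = 50(1 − m)²
- answered surveys discarded = 100(1 − m) − 100(1 − m)²

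At m = 0.10 this gives 50 × 0.81 = 40.5 pairs and 90 − 81 = 9 discarded. At m = 0.20 it gives 50 × 0.64 = 32 pairs and 80 − 64 = 16 discarded. A block left unfilled at the end of a stratum would be lost as well.

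Simulated power for a true difference of 0.566 SD (30,000 trials per cell), block-paired test against Welch test on all answered surveys:

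| Within-block correlation | 10% missing | 20% missing |
|---|---|---|
| 0 | 69.5% vs 75.1% | 58.6% vs 70.0% |
| 0.1 | 74.2% vs 76.4% | 63.7% vs 71.4% |
| 0.2 | 79.2% vs 77.7% | 68.8% vs 71.8% |

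At 5% missing a smaller simulation (6,000 trials per cell) gave 75% vs 78%, 78% vs 78% and 83% vs 80% at correlations of 0, 0.1 and 0.2. The loss therefore depends on the missing rate and on how alike block members are. It can be nil or reversed.

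**Pairs formed arbitrarily across arms.** Nothing in the plan suggests this, but software asked for a paired test on two columns of data would do it.

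- Simulated type I error is 5.1%, and power is 79.0% against 79.8% for Welch (40,000 trials), so error rates barely move.
- The result does depend on the pairing chosen. Data with a two-sample p of 0.050 gave paired p values from about 0.024 to 0.085 over the central 95% of random pairings.
- The test cannot be run on arms of unequal size. The arms had unequal numbers of answered surveys in 87% of simulated trials at 10% missing and 90% at 20%.

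**Reading 3, separate tests within each arm.** Suppose both arms truly change by the same amount d. Let p be the power of a one-arm paired t-test with n = 50 (noncentral t, 49 degrees of freedom). The chance that exactly one arm is significant is 2p(1 − p):

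| d | 0 | 0.1 | 0.2 | 0.28 | 0.4 | 0.5 |
|---|---|---|---|---|---|---|
| p | 0.050 | 0.107 | 0.284 | 0.492 | 0.792 | 0.934 |
| exactly one significant | 9.5% | 19% | 41% | 50% | 33% | 12% |

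For example, at d = 0.2: 2 × 0.284 × 0.716 = 0.41. The value 0.28 is close to the worst case, because 2p(1 − p) peaks at p = 0.5. Change in both arms is plausible: every patient gets a tracker, exercise advice and a chosen step goal (sections 3.1 and 4.3), and controls get daily step feedback (section 4.5.1).

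**The case against.** The strongest reply is that this is an obvious slip. The sentence says that the arms will be compared, so a two-sample test on change must be meant, and then no estimate or sample size alters. For the same reason reading 3 sits badly with the sentence, and its most striking figure, 50%, belongs to a near-worst case. Both points are fair. They lower the likely harm but do not make the named test correct, and the text does not settle which analysis is meant.

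A second reply is that blocks of 2 supply the pairs. They could, but they appear in the plan only as an allocation device, and no rule is given for incomplete blocks.

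A third is that few surveys may be missing. Section 3.1 permits telephone collection, and section 4.7 pays $25 at each follow-up point, conditional on the survey and on step data for at least 60% of days. Both may help, and at 5% missing the cost of block pairing is small or absent. That stands as a limit on the size of the loss.

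Finally, a Welch test on answered surveys also leaves out non-responders, so it does not fully meet the commitment to analyse all consented patients either. This is true. Block pairing would discard the answered surveys of their block partners as well.

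**Conclusion.** The concern holds. Section 5.3 names a paired test for a comparison of two independent groups and defines no pairs. The error is confined to secondary outcomes 4 to 6; the primary outcome and the step and activity outcomes use mixed models and are untouched.

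If the sentence is a slip, the cost is ambiguity only. If block pairing is meant, the power loss under the assumptions above runs from none to about 11 percentage points (70.0 − 58.6 = 11.4 at 20% missing and no within-block correlation). If within-arm tests are meant, there is no between-arm test, and one arm may appear to improve and the other not in up to about half of trials with no true difference.

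The defect in the wording is certain. The sizes rest on assumed missing rates, correlations and changes, because the documents give none for the surveys. It should be corrected before analysis, but it does not threaten the trial's main conclusion.

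**What to change.** In section 5.3, replace the paired t-tests with independent two-sample (Welch) t-tests on change from baseline, reporting the mean difference between arms and its 95% confidence interval for each score and time point. Label any within-arm paired tests as descriptive. If block pairing really is intended, say so and give the rule for incomplete blocks.

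An optional gain in efficiency, not needed to correct the error, is ANCOVA with arm, the baseline value of the score and the baseline-step stratum. If the score has equal variance at baseline and follow-up, with correlation rho between them, adjusting for baseline gives a variance of (1 + rho)/2 times that of the change-score analysis. At assumed rho of 0.5, 0.7 or 0.8 the ratio is 0.75, 0.85 or 0.90, so the standard error is 13%, 8% or 5% lower. This would depart from the plan's stated choice not to adjust, so it is for the investigators to decide.

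The cost is one sentence in the analysis section. No new data are needed.

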5.1 Primary and secondary outcome measures

The study's primary outcome measure will be change in daily step count from baseline to the intervention period for patients in the intervention arm versus patients in the attention control arm.

Secondary outcome measures will include:

- 1) Change in daily step count from baseline to the follow-up period
- 2) Change in daily number of minutes engaged in light, moderate, or vigorous physical activity from baseline to the intervention period, and from baseline to the follow-up period
- 3) Change in daily number of minutes engaged in moderate, or vigorous physical activity from baseline to the intervention period, and from baseline to the follow-up period
- 4) Change in Walking Impairment Questionnaire score from baseline to the end of the intervention period, and from baseline to the end of the follow-up period
- 5) Change in PROMIS mobility, pain interference, and satisfaction with social roles and activities scores from baseline to the end of the intervention period, and from baseline to the end of the follow-up period
- 6) Change in SF-36 physical functioning scale from baseline to the end of the intervention period, and from baseline to the end of the follow-up period

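### The ten patient-reported comparisons drop anyone with a missed survey, although 5.3 promises all patients and intention-to-treat, because imputation covers step values only

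*Combined protocol and SAP*

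**What the plan says.** All references are to the combined protocol and SAP.

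- **Analysis set (5.3):** "Data for all consented patients, whether or not they completed all protocol requirements, will be included for analysis". The next paragraph adds: "All analyses will be performed using intention-to-treat".
- **Missing data (5.3):** missingness is described for tracker days only: "Data can be missing for any day if the participant did not use the activity tracking device or did not upload data". The method is "we will use multiple imputation for step values that are either missing or for values less than 1000 steps", with five imputations combined by Rubin's rules. The sensitivity analyses also concern step values only.
- **Survey test (5.3):** one method is given for the survey scores at both follow-up times: "we will compare the intervention and control arms using paired t-tests, without adjustment for baseline characteristics".
- **Survey outcomes (5.1, items 4 to 6):** the first is "Change in Walking Impairment Questionnaire score from baseline to the end of the intervention period". The others are three PROMIS scores and SF-36 physical functioning. Each is also assessed at the end of follow-up.
- **Collection (4.6):** at week 16 "patients will be alerted by the Way to Health platform to return to the website to complete an end-of-study questionnaire", and the same questionnaire is repeated eight weeks later. Section 3.1 also allows collection by telephone. Section 4.7 pays $25 at each follow-up survey, on condition that step data exist for at least 60% of days.

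**The concern.** The set of patients that 5.3 promises is not the set that its survey test can use. A change score needs both surveys, and nothing in the plan supplies a missing one. A patient may lack a follow-up survey through withdrawal (allowed at any time, 4.1), through being stopped after the investigator's review of a reported problem (6.5), or through not responding.

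Among the outcomes listed in 5.1, items 4 to 6 are the only ones that measure function or symptoms; the others come from the tracker. Section 3.1 gives improved functional capacity as the aim of the trial. The plan protects the step data against missingness and leaves these scores unprotected.

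Loss could also differ by arm. Controls receive a daily step-count text (4.5.1). Intervention patients also have coaching texts, points, levels, a supportive sponsor and staff calls (4.5.2). The link between engagement and survey completion may therefore not be the same in the two arms.

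**Working it through.** **1. Comparisons affected.** Walking Impairment Questionnaire (1) + PROMIS (3) + SF-36 physical functioning (1) = 5 scores. At two times, 5 × 2 = 10. This counts the Walking Impairment Questionnaire as one score, as 5.1 words it; separate subscales would raise the count.

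**2. A patient with no week-16 survey, followed through 5.3.** The analysis-set sentence includes this patient. The imputation sentence does not reach the score, because it is limited to step values. The t-test needs a week-16 change, which does not exist, so the patient leaves that comparison but may return for week 24. Replacing the paired test with a two-sample test, or adding the baseline score, would not bring the patient back.

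**3. The plan's only power figure.** Section 5.2 states 80% power for 1,100 steps with 50 per arm. With SD 2,000, two-sided alpha 0.05 (sidedness assumed) and a normal approximation: 1,100 / (2,000 × √(2/50)) − 1.96 = 2.75 − 1.96 = 0.79, and Φ(0.79) = 78.5%. That is within two points of 80%. No power is stated for the surveys. The figure is used here only for scale: 1,100 / 2,200 = 0.5 SD, where 2,200 is the midpoint of the two SDs in 5.2 (about 2,000 and 2,400).

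**4. Precision lost (non-response rate assumed).** Difference detectable with 80% power = 2.80 × √(2/n):

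| Missing per arm | n per arm | Detectable difference (SD) |
|---|---|---|
| 0% | 50 | 0.560 |
| 10% | 45 | 0.591 |
| 20% | 40 | 0.626 |
| 30% | 35 | 0.670 |

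**5. Bias, simplest form.** Suppose non-responders change g SD less than responders, and the missing fractions are m₁ (intervention) and m₀ (control). The complete-case bias is g(m₁ − m₀). With g = 0.5, 20% against 10% gives 0.05 SD and 30% against 10% gives 0.10 SD. Equal fractions give none.

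**6. Bias when completion rises with step change.** All inputs except the 0.5 SD step effect are assumptions.
- Step change z is normal with SD 1 and mean μ, which is 0 in controls and 0.5 in the intervention arm.
- Score change has SD 1 and correlation r with z, so the true difference is 0.5r.
- P(survey completed) = logistic(logit(c) + slope × z), with c = 0.7, 0.8 or 0.9.
- The complete-case difference is r(M₁ − M₀), where M = ∫zφ(z−μ)p(z)dz / ∫φ(z−μ)p(z)dz in each arm.

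Numerical integration gives:

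| Slopes (control, intervention) | r = 0.5, true 0.25; c = 0.7 / 0.8 / 0.9 | r = 0.3, true 0.15; c = 0.7 / 0.8 / 0.9 | Bias range (SD) |
|---|---|---|---|
| 1, 1 | 0.216 / 0.222 / 0.231 | 0.130 / 0.133 / 0.139 | −0.034 to −0.011 |
| 1.5, 0.5 | 0.122 / 0.143 / 0.175 | 0.073 / 0.086 / 0.105 | −0.128 to −0.045 |
| 0.5, 1.5 | 0.310 / 0.300 / 0.285 | 0.186 / 0.180 / 0.171 | +0.021 to +0.060 |

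Completion in these scenarios is about 65% to 91% by arm. The standard error, √(1/n₀ + 1/n₁) with n = 50 × completion, is 0.21 to 0.24. The worst case is 0.128 / 0.241 = 0.53 standard errors. Simulations of the same set-up agree within Monte Carlo error; with equal slopes they show bias of up to about 0.04.

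**7. What using the step data achieves.** In the simulations, a regression on z in all patients returned the true difference to within about 0.01 SD. That result is built in, because completion depends on z alone and z is observed for everyone. At r = 0.3 the root mean squared error hardly changed (0.251 and 0.255 with c = 0.7 and slopes steeper in controls).

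**8. A mixed model of the two follow-up scores.** This was simulated with r = 0.5, true difference 0.25, residual correlation 0.6 between visits, c = 0.7, slopes steeper in controls and 800 replicates. Week-16 completers gave about 0.13. The mixed model gave 0.126 when the same patients missed both surveys, and 0.151 when misses were independent given step change.

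**The case against.** The strongest reply has four parts.

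- **Intention-to-treat may only mean analysis as randomised.** On that reading it does not prescribe how missing outcomes are handled. This is fair for that sentence alone. It does not settle the point, because the sentence on including patients whether or not they completed the protocol is explicit, and the survey test cannot honour it.
- **The loss may be small.** Telephone collection (3.1) and payment on the same terms in both arms (4.7) both work against non-response, so failing to return to the website need not mean a missing survey. This stands as a limit on the size. Neither section gives a rule for a survey that is still missed.
- **The bias rests on assumptions.** The documents give neither a completion rate nor a correlation between steps and scores. Material bias appears only when the dependence on steps differs threefold between arms, and its sign reverses when the arms are swapped. This stands too. A reader might infer that the survey results will be materially biased, or biased in favour of gamification. The documents support neither.
- **Only secondary outcomes are affected.** This is correct. The primary step-count outcome has imputation and sensitivity analyses, so the point does not extend to it.

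**Conclusion.** The point holds. Followed as written, 5.3 gives ten complete-case comparisons, one analysis set per time point, and not the inclusive set it announces. This is more than a missing detail, because the stated test does not deliver the stated analysis set.

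The size is modest and cannot be derived from the documents. Under the assumed scenarios the bias is about 0.01 to 0.03 SD with equal dependence on steps. With strongly unequal dependence it reaches about 0.13 SD towards zero, or 0.06 SD away from it, against a standard error of 0.21 to 0.24 SD. The change should be made, but the trial's main conclusion does not depend on it.

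A reader might also infer that any model using both follow-up visits would cure the problem. It would not: a patient with neither survey adds no outcome to a mixed model of the two scores, and that model ignores the step data.

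**What to change.** In 5.3:

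1. Extend the planned multiple imputation to the five survey scores at weeks 16 and 24, in all randomised patients. Use arm, baseline score, the other follow-up score and the patient's mean step count in the corresponding period. The set should be randomised rather than consented patients, because those who fail the run-in are never randomised (4.3).
2. Compare the arms in each imputed data set with a between-arm analysis (two-sample or baseline-adjusted), and combine by Rubin's rules.
3. Report survey completion by arm at each time.
4. Keep the complete-case between-arm comparison as a sensitivity analysis.

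The cost is SAP wording and a little programming; no new data, visits or patients are needed. The downsides are that the method assumes data missing at random given scores and steps, helps less for patients who also stop wearing the tracker, and may give slightly wider intervals.

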4.2. Baseline Questionnaire

After providing informed consent, participants will complete an online questionnaire to confirm eligibility and complete the study surveys.

The baseline survey will consist of the San Diego Claudication Questionnaire and the Walking Impairment Questionnaire to characterize limb symptoms and functional limitations,^{23,24} the Patient-Reported Outcomes Measurement Information System (PROMIS) measures of mobility, pain interference, and satisfaction with social roles and activities,²⁵ and the SF-36 physical functioning scale.²⁶ Patients will also complete several questionnaires to obtain a psychometric profile: the Big Five Inventory survey to evaluate personality characteristics, the Grit Scale to assess perseverance, the Self Efficacy for Exercise Behaviors survey, the PHQ-9 questionnaire to assess mental health state, and the MOS Social Support survey.

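### The ten survey-score comparisons leave out each score's own baseline as a covariate, which gives up precision the trial could have at no cost

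*Combined protocol and SAP*

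**What the plan says.** The last paragraph of section 5.3 sets out the survey analysis, and its scope is given as: "For changes in survey measure scores from baseline to the end of the intervention, and from baseline to the end of follow-up". The method named there for comparing the two arms is a paired t-test, to be run "without adjustment for baseline characteristics". Section 5.1 lists the scores as secondary outcomes: "Change in Walking Impairment Questionnaire score from baseline to the end of the intervention period", then "Change in PROMIS mobility, pain interference, and satisfaction with social roles and activities scores", then SF-36 physical functioning. Each is assessed at the end of the intervention and at the end of follow-up.

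Every baseline value is available. Section 4.2 states that "The baseline survey will consist of the San Diego Claudication Questionnaire and the Walking Impairment Questionnaire", and goes on to the three PROMIS measures and the SF-36 scale. Section 4.6 repeats the same instruments at week 16 and again 8 weeks later.

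Two other passages give context. The step-count model in section 5.3 includes the participant's baseline steps as a covariate. Section 4.4 describes randomization as "stratifying on baseline step count", and no survey score is a stratification factor.

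**The concern.** For the step outcome the plan uses the baseline value as a covariate. For the survey outcomes it does not, and it gives no reason. A comparison of raw change scores fixes the coefficient on baseline at 1. When baseline and follow-up correlate at less than 1, that over-corrects. The interval is wider than the data require, and the arm that happens to start worse will tend to appear to improve more.

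The survey scores are the patient-reported measures of function, pain interference and social participation among the outcomes in section 5.1. The trial has 100 patients and no power statement for any of these scores, so avoidable variance matters.

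**Working it through.** **Inputs from the documents.** Five scores (WIQ counted as one, PROMIS as three, SF-36 physical functioning as one) at two time points: 5 × 2 = 10 comparisons. Sample size is 50 per arm (section 5.2).

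**Inputs assumed.** r is not given, so 0.4 to 0.9 is shown. The score variance σ² is taken as equal at baseline and follow-up, and every patient is taken to complete the surveys. Alpha is 0.05, two-sided (section 5.2 does not state the sidedness).

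**The plan's own figure.** Section 5.2 gives power for steps only: 80% for a difference of 1100. With SD 2000, SE = 2000 × √(2/50) = 400, 1100/400 = 2.75, and power = Φ(2.75 − 1.96) = 78.5%, close to the stated 80%. With SD 2400 it is 63.0%. Neither figure bears on the surveys, for which there is nothing to reproduce.

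**Formulas, for a two-sample comparison.**
- Per-patient variance of change: 2σ²(1−r).
- Per-patient variance after ANCOVA on baseline: σ²(1−r²).
- Ratio, ANCOVA to change: (1−r²)/[2(1−r)] = (1+r)/2.
- Shift in the change-score difference from a baseline difference d: −(1−r)d. Under ANCOVA it is about 0.
- One standard error of chance baseline imbalance: √(2/50) = 0.2 SD.
- Difference detectable with 80% power, in SD units: (1.96 + 0.84) × 0.2 × √(per-patient variance/σ²).

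| r | Variance ratio | SE ratio | Equivalent extra patients (1/ratio − 1) | Shift from 0.2 SD imbalance, change score | Detectable difference, change / ANCOVA |
|---|---|---|---|---|---|
| 0.4 | 0.70 | 0.84 | 43% | 0.12 SD | 0.61 / 0.51 SD |
| 0.5 | 0.75 | 0.87 | 33% | 0.10 SD | 0.56 / 0.49 SD |
| 0.7 | 0.85 | 0.92 | 18% | 0.06 SD | 0.43 / 0.40 SD |
| 0.8 | 0.90 | 0.95 | 11% | 0.04 SD | 0.35 / 0.34 SD |
| 0.9 | 0.95 | 0.97 | 5% | 0.02 SD | 0.25 / 0.24 SD |

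For illustration, with a true difference of 0.5 SD (an assumption; the documents give none), power rises from 63% to 78% at r=0.4, 71% to 82% at r=0.5, and 90% to 94% at r=0.7.

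**Simulation check.** With 50 per arm and 20,000 replicates, the variance ratios were 0.66, 0.75, 0.86 and 0.91 at r = 0.3, 0.5, 0.7 and 0.8. The closed form gives 0.65, 0.75, 0.85 and 0.90; the small excess is the price of estimating the slope. The change-score difference moved with baseline imbalance at slopes of −0.70, −0.50, −0.30 and −0.20. The ANCOVA slopes were about 0.

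**Unequal variances.** With SDs s₀ at baseline and s₁ at follow-up, the change-score variance minus the ANCOVA variance is s₀² + s₁² − 2rs₀s₁ − s₁²(1−r²) = (s₀ − rs₁)². This is never negative, so the direction of the result does not need equal variances; only the size does.

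**The case against.** The strongest reply is that a change score already deals with baseline and that a two-sample test on change is valid. Much of this stands. A reader might infer that the whole of any baseline imbalance stays in the result, or that the estimate is biased. Neither is so: baseline has been subtracted, what remains is the fraction (1−r) with opposite sign, and over repeated randomizations the estimate is unbiased.

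A second reply is that baseline characteristics may mean demographic and clinical variables, so the plan does not clearly reject a baseline-score term. That is a fair reading, but it changes nothing: a t-test on change has no such term either way. The covariate-adjusted secondary analyses in section 5.3 follow the physical-activity models, and no adjusted survey analysis is specified.

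Third, the plan names paired tests. The figures above apply only to a two-sample comparison. A paired test within each arm would give no between-arm estimate for them to describe. The precision point therefore comes after that correction, and a single edit should settle both.

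Fourth, the size depends on an assumed r and becomes small as r approaches 1. This stands, which is why the table runs to 0.9.

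Three further inferences should not be drawn:
- That ignoring the step strata invalidates the test. Leaving a stratification factor out of the analysis is generally conservative.
- That patients with a missing survey will be dropped despite "All analyses will be performed using intention-to-treat". The plan specifies imputation for step values and does not say how missing survey scores are handled, so this would be inference.
- That these are the trial's only measures of function. Section 3.1 frames the trial around functional capacity, and steps and activity minutes are also outcomes.

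**Conclusion.** The point holds as a recommended improvement. Ten secondary comparisons omit a covariate that the trial already collects. Adjustment would reduce the variance of the arm difference by 30% at r=0.4, 15% at r=0.7 and 5% at r=0.9, and would remove the residual effect of chance baseline imbalance (0.12, 0.06 and 0.02 SD respectively for an imbalance of one standard error). These sizes assume a two-sample comparison, equal variances, complete surveys from 50 per arm, and a value of r that the documents do not supply. The primary outcome is unaffected, and the unadjusted two-sample comparison would still be valid.

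**What to change.** Replace the survey sentence in section 5.3 with text along these lines: each survey score at week 16 and at week 24 will be compared between arms by ANCOVA, with terms for arm, the baseline value of the same score and the randomization step stratum; the adjusted arm difference will be reported with its 95% CI at each visit.

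An equivalent alternative is one repeated-measures model per score over both visits, with arm by visit, baseline score by visit and stratum. It uses whichever follow-up survey a patient completed, but does not recover patients who miss both. The handling of missing survey scores should be stated with either model.

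The cost is one sentence, with no new data and no more patients. The same sentence resolves the paired-test wording, so the two should be corrected together.
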